## F. Risk/benefit assessment:

1. Physical risk: The potential risks for this study are minimal. There is a slight risk of discomfort, bruising and infection with blood draw. Blood will be drawn by trained research staff. IVs will be placed and blood draws will be conducted by an RN or LPN. Sterile instruments will be used for blood draws, the participants skin will be cleaned with an alcohol wipe at the site of the needle stick. Participants will complete no more than two study visits in a seven-day period.
2. Psychological risk: Risks for participants include those associated with the inconvenience of participation including answering surveys, providing blood samples, and completing multiple visits. To minimize the inconveniences associated with study participation we will review all data collection instruments and study procedures to minimize the number of items in our instruments and improve the accessibility and convenience of our study procedures. We may use several methods to enhance convenience to participants, including offering study visits throughout the day. Another risk is feeling pressured to be in the study, which we will track in order to monitor and will report as an adverse event. Finally, although very unlikely, some questions may make participants uncomfortable; participants are not required to answer questions they do not wish to.
3. Social risk: None
4. Economic risk: None
5. Potential benefit of participating in the study
  - a. There are no direct benefits to participants for participating in this study
  - b. If shown to be effective, our study could, in the future, benefit smokers with COPD who are unable to quit smoking using FDA-approved medications by helping them switch to a potentially less harmful product.

- c. The researchers hope that the information gathered from this research may be useful in informing interventions for smokers unable to quit and to therefore benefit public health.

**G. Location where study will be performed:** All study visits will be completed at the Clinical Research Unit – Rainbow. During study visits where cardiovascular functioning is measured, participants will also visit [name] laboratory (KUMC campus; [name]). All data will be directly entered into an electronic data capture system (i.e., RedCap or CRIS), therefore minimizing the use of paper records. If paper records are generated, they will be stored in locked file cabinets. Only study staff will have access to the locked records and the secure online electronic data capture system.

**H. Collaboration (with another institution, if applicable):** N/A

**I. Single IRB Review for a Multi-site study (if applicable):** N/A

**J. Community-Based Participatory Research (if applicable):** N/A

**L. Assessment of Subject Safety and Development of a Data and Safety Monitoring Plan**

1. Elements of the plan include:

The current study does not pose more than minimal risk. We continue to closely monitor the situation. To address this concern, we will obtain informed consent, closely monitor AEs and SAEs and promptly report any that occur. [name] will provide medical oversight. The Evolv Reflex EC will be used for the proposed study. The Reflex device is a commercially available pod-based device and is compatible with nicotine salt and freebase nicotine e-liquid. We will use commercially available nicotine salt e-liquid in ~5% nicotine concentration. If participants cannot tolerate the Evolv Relfex, we will offer

a choice of JUUL or Vuse devices. JUUL and Vuse are pod based systems. We will offer menthol or tobacco flavors in 5% or 3% concentration.

2. We will protect participants and minimize risks by using the strict exclusion criteria and careful monitoring of AEs. AEs will be tracked during regularly scheduled visits or through spontaneous reports made by participants. Drs. [name], [name], and [name] will be made aware of unexpected or serious AEs within 24 hours of the first report by participants; all other AEs will be reviewed weekly by [name] and discussed at regular meetings with [name]. SAEs will be reported to the KUMC IRB within 24 hours of first awareness of the event. Unexpected adverse events that are related to the study products will be reported to KUMC IRB within 5 working days of first awareness of the event if the event is not serious and within 24 hours of first awareness if the event is serious. Unexpected adverse events that are unrelated to the study products will be reported to the KUMC HSC during yearly routine event reporting. [name] will determine relatedness for each reported AE. SAEs will be defined as any event experienced by a study subject while using the study device that is fatal, life-threatening (subject was at risk of death from the event as it occurred), disabling or incapacitating, requires inpatient hospitalization or prolongs a current hospitalization, or required intervention to prevent permanent impairment or damage.
3. In the case of AEs, participants will be reminded of the voluntary nature of the study and be allowed to discontinue participation without negative consequences. In the case of SAEs related to use of study products, participation will be discontinued.
4. We will follow up with participants three months post treatment.

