using the Tiffany-Drobes Questionnaire on Smoking Urges – brief (QSU-brief) and Minnesota Nicotine Withdrawal Scale (MNWS) pre- and post-session. The mCES will assess subjective effects and sensory experiences at the end of each session. Participant's intentions for future use (e.g., purchase, use) of ECs will be assessed using a 4-item measure. At the end of the baseline vaping session, participants will be randomized and enrolled (stratified on EC history) to one of three study arms in a 1:1:1 fashion: 1) Brief Advice, 2) Single Episode Training, 3) Enhanced EC Training. See the Training Guild for Researcher for specific training. For the Brief Advice study arm, participants will be given brief advice to switch to the EC and basic instructions on use of the EC and refilling pods. Participants will view their topography post-intervention via the Escribe software while they puff. Based on our preliminary data, trained research staff will give feedback on puff parameters shown to differ between complete switchers and switch "failures" – puff duration, flow rate, inter-puff interval, and puff number. The session will last ~30 minutes. For the Enhanced EC training study arm, participants will receive the same training as the Single Episode Training arm. Participants will be asked to set a switch date using the Action Planning form. Participants will take the EC device home and use it as much or as little as they would like before the next visit. Lung function will be assessed via spirometry. At the end of the visit, a 6-minute walk distance (6MWD) test will be done to assess the participant's overall ability to conduct everyday activities. Baseline cardiovascular functioning will be measured using Pulse Wave Velocity, a sensitive measure of arterial stiffness that shows rapid (~1 month) changes with switching to ECs. Baseline beat-to-beat blood pressure will be measured to assess blood pressure and vascular elasticity. Participants will be compensated \$50 for this visit.

- d. **Human Lab Visit 2 / RCT Visit – Week 0 (1-5 days after Human Lab Visit 1):** Human Lab Visit 2 will occur 1-5 days after Human Lab Visit 2. Human Lab Visit 2 will be identical to Visit 1 but will not include any training, 6MWD test, or cardiovascular assessment. The purpose of this visit is to assess changes in topography following training at visit 1. Participants will be compensated \$50 for this visit.

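### The SAE definition is tied to study-device use and has no observation window, and two reporting sentences disagree for unexpected, unrelated serious events

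*Protocol*

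**What the plan says.** All the safety text is in Protocol section II.L.

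- **Definition (item 2).** "SAEs will be defined as any event experienced by a study subject while using the study device", provided the event is also fatal, life-threatening or disabling, involves a hospital admission, or needs intervention to avert lasting harm. There is no other SAE definition, and no start or end of the observation period.
- **Collection (item 2).** "AEs will be tracked during regularly scheduled visits or through spontaneous reports made by participants". Device use is not a condition here.
- **Internal notice (item 2).** Named study roles "will be made aware of unexpected or serious AEs within 24 hours of the first report by participants".
- **SAEs to the IRB (item 2).** "SAEs will be reported to the KUMC IRB within 24 hours of first awareness of the event", with no qualifier for relatedness or expectedness.
- **Unexpected and related (item 2).** To the IRB within 5 working days if not serious, and "within 24 hours of first awareness if the event is serious".
- **Unexpected and unrelated (item 2).** "Unexpected adverse events that are unrelated to the study products will be reported to the KUMC HSC during yearly routine event reporting". Serious events are not excepted.
- **Follow-up (item 4).** "We will follow up with participants three months post treatment". The last item of the Study Procedures (section II.E.2) has monthly phone calls for the same three months.

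On exposure, the Visit 1 procedures (section II.E.2, item c) let participants take the device home and "use it as much or as little as they would like before the next visit". Participants are also asked to abstain from nicotine for 12 hours before the human lab visits.

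**The concern.** An SAE definition normally asks only how severe the outcome was and whether it fell inside the observation period. Whether the product caused it is a separate judgement. Section II.L otherwise follows that division: relatedness is decided for each reported event, and a later item speaks of SAEs that are related to the study products, which implies that unrelated SAEs exist. Making device use part of the definition blurs the two steps.

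The sample is people with COPD who smoke, some of whom will go back to cigarettes or use the study device very little. A hospital admission in such a person, or in someone no longer using the device during follow-up, does not meet the definition. It then depends on the other reporting sentences, and one of those is itself out of step with the 24-hour rule.

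There is also a statistical side. Device use occurs after randomisation, and the training is meant to change it. A safety count conditional on such a variable need not mean the same thing in each arm.

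**Working it through.** No arithmetic applies. The check sets the sentences side by side.

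**Step 1: what the definition covers under each plausible reading of its device-use condition.**

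| Reading | Participant who stops before Week 12 | Three-month follow-up |
|---|---|---|
| During actual use | Not covered once off the device | Covered only if still using it |
| During that person's own period of use | Not covered after stopping | Covered only if still using it |
| While the device and pods are supplied (12 weeks) | Covered to Week 12 | Not covered |

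No reading covers the whole of study participation. On the strictest reading, even the abstinence required before lab visits is time off the device.

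**Step 2: which external reporting sentence applies to a serious outcome.**

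| Serious outcome | On the device (an SAE) | Off the device (not an SAE by the text) |
|---|---|---|
| Unexpected, related | 24 h to IRB under both sentences: consistent | Related-event sentence; 24 h only if its word for serious is read independently of the SAE definition |
| Unexpected, unrelated | 24 h to IRB **and** yearly to HSC: timing and recipient differ | Only the yearly HSC sentence clearly applies |
| Expected, related | 24 h to IRB | No external sentence applies |
| Expected, unrelated | 24 h to IRB | No external sentence applies |

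Among events that meet the definition, the sentences disagree in one cell of four: unexpected and unrelated. Off the device, the general 24-hour IRB sentence drops out of every row.

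**Step 3: is the omission in the unrelated-event sentence visible from its neighbour?** Yes. The related-event sentence gives different deadlines for serious and non-serious events. The unrelated-event sentence makes no such split.

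**Step 4: does device use plausibly differ by arm?** H2a (section I.A, Aim 2) predicts the largest share of predominant EC users with enhanced training, then single-session training, then brief advice. If that holds and the definition is read as actual use, the arm with more use has more time in which an event can qualify. This is a direction only; the protocol gives no amount of use per arm.

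**The case against.** The strongest reply is that little is lost in practice. Adverse events are collected at visits and by spontaneous report without regard to device use, unexpected or serious ones reach the study leads within 24 hours, and relatedness is judged for every report. This stands. A reader might infer that off-device serious events go unrecorded, and the text does not support that. What is lost is the SAE label and the clear 24-hour IRB route.

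Second, the definition may simply mean the supply period. All three arms receive the device and pods for 12 weeks, so the window would then be equal across arms and the comparability concern would fall away. That is a fair reading, but the text does not state it, and it still leaves out the three-month follow-up. A reader might go further and infer that a planned safety comparison is biased. Sections V.A and V.B plan no between-arm SAE comparison, and H2a concerns predominant use, not stopping. Comparability is therefore a conditional concern about any count by arm that is made.

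Third, the two reporting sentences can both be obeyed, since neither says that it is the only route. That is correct, so this is an ambiguity rather than a strict impossibility. But staff who rely on the yearly sentence alone would report an unexpected, unrelated, serious event on a different schedule and to a differently named body. The clash does not extend to all unrelated serious events: expected ones fall under the 24-hour sentence only.

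Finally, a reader might infer that about half of observation time lies outside the definition, taking roughly 13 weeks of follow-up against 12 of treatment: 13 / (12 + 13) = 52%. This assumes that device use ends at Week 12. Pods are returned and weighed, but nothing says that the device is handed back, and someone still using it would be covered on the literal wording. The ratio also leaves out the time before Week 0, when participants already have the device at home.

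**Conclusion.** The point holds in a limited form. The SAE definition is conditional on device use and has no window, so serious events off the device fall outside it and lose the 24-hour IRB route, although they are still tracked as adverse events. On every plausible reading, some of the three-month follow-up is or may be uncovered. Separately, the reporting sentences need reconciling for one class of event: serious, unexpected and unrelated.

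The size is one of classification and timing. It cannot be turned into a number or share of events, because the documents give neither an SAE rate nor the time spent off the device. The loss of comparability between arms rests on two assumptions: that the definition means actual use, and that use differs by arm as H2a suggests. The conclusion on the definition itself needs neither. The change should be made; it is a correction of wording in a 45-participant pilot and leaves the efficacy analyses untouched.

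**What to change.** - Define an SAE by the seriousness criteria already listed, over a stated window that covers all study participation and includes the three-month follow-up, regardless of device use.
- Record device use at onset as a variable, so that events on and off the device can be told apart later. For participants on JUUL or Vuse this would rest on self-report, since the protocol says that those devices store no data.
- Reconcile the 24-hour IRB sentence and the yearly HSC sentence for unexpected, unrelated, serious events, so that each such event has one stated deadline and recipient. Which of the two should govern is for the sponsor and the board to settle.

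The cost is a short protocol amendment, one extra data field and a few more reports. No change to visits, sample size or analysis is needed. How SAEs are summarised can be left to the SAP.

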**Dual Users:**

Use of tobacco products other than cigarettes and e-cigarettes in the past 30 days, current use of cessation medications, pregnant, planning to become pregnant, or breastfeeding, recent history of cardiovascular or pulmonary events in the past 3 months, household member current or previously enrolled in the study

3. Withdrawal/Termination criteria:

Participants will be instructed to present to the lab nicotine deprived (12 hours abstinent) for the first study visit. If participants present to the first study visit with an eCO  $>12$  ppm or they report other nicotine use on two separate study visits, they will be withdrawn from the study (i.e., participants will be rescheduled one time).

4. Participants will not be allowed to participate in another research study that aims to alter their tobacco use during this research study.

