### **RANDOMIZED TRIAL OF EC TRAINING**

#### **RCT Assessments (see Table 1 for timing):**

**Cigarette smoking.** Cigarette smoking will be assessed at W0, W4, W8, and W12 using the Timeline Followback (TLFB) in which individuals report on number of cigarettes per day (CPD) in the past 7 days.

**eCO** levels will be used to biochemically confirm smoking status. eCO  $<6$  ppm will indicate a complete switch.

**Respiratory health and lung function.** The COPD assessment test (CAT) is a COPD-specific 8-item questionnaire designed to assess impairment in health status of COPD patients. Participants will complete the CAT at baseline and Wks 4, 8, and 12 to assess changes in self-reported respiratory health. Lung function will be assessed via spirometry.

Measure	Table 1. Measures by timepoint					
	SCRN	V1	Human Lab	W4	W8	RCT
Topography*		X	X	X	X	X
Nicotine boost		X	X			X
eCO	X	X	X	X	X	
7-day TLFB	X	X	X	X	X	X
Health effects						
Spirometry		X				X
COPD Gold Staging	X					X
CAT	X			X	X	X
Pulse wave velocity		X				X
Beat to beat blood pressure		X				X
6MWD		X				X
Other self-report						
Cigarette craving/withdrawal		X	X			X
mCES				X		X
Subjective effects of EC		X	X			X
Behavioral intentions	X			X		X

*Notes.* Topography measured throughout 12-week switching period

**6-minute walk distance** (6MWD) will assess changes in functional activity. The 6MWD assesses an individual's overall ability to conduct everyday activities and will be conducted at baseline, W4 and W12. This measure is particularly responsive to change in smokers with COPD. Specifically, improvements in 6MWD have been found within xx weeks of smoking reduction in smokers with COPD [ref].

**Changes in cardiovascular functioning** will be measured using Pulse Wave Velocity, a sensitive measure of arterial stiffness that shows rapid (~1 month) changes with switching to ECs, at baseline and W12. In addition, we will assess changes in beat-to-beat blood pressure from baseline to W12. Beat-to-beat blood pressure is a sensitive measure of blood pressure and vascular elasticity. Measures of cardiovascular functioning will be conducted by [name] and her team. These measures are sensitive to changes in smoking and vaping status and are associated with downstream health outcomes that result from smoking, such as cardiovascular disease.

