- j. **RCT Visit – Week 12:** Participants will smoke and vape as they normally would. Participants will complete eCO measurement to confirm smoking status. Because the eCO is the only measure needed for this visit, visit location will be flexible. Visits will be conducted as determined by location and abilities of the study participant. Participants will be compensated \$10 for this visit.
- k. **Human Lab Visit 3:** Human Lab Visit 3 (Week 12) will be identical to Visit 1 (above) but will not include any training. The visit is intended to measure longer-term changes in EC puff patterns. Participants will be instructed to remain abstinent from nicotine and tobacco for 12 hours prior to the study visit. Participants will complete eCO measurement to confirm tobacco/nicotine abstinence. To assess changes in self-reported respiratory health, participants will complete the CAT. Lung function will be assessed via spirometry. Self-reported levels of cigarette craving and withdrawal will be measured using the Tiffany-Drobes QSU-brief and MNWS. The mCES will assess subjective effects and sensory experiences at the end of each session. Participant's intentions for future use (e.g., purchase, use) of ECs will be assessed using a 4-item measure. At the end of the visit, a 6-minute walk distance (6MWD) test will be done to assess the participant's overall ability to conduct everyday activities. Baseline cardiovascular functioning will be measured using Pulse Wave Velocity, a sensitive measure of arterial stiffness that shows rapid (~1 month) changes with switching to ECs. Baseline beat-to-beat blood pressure will be measured to assess blood pressure and vascular elasticity. Participants will be compensated \$50 for this visit.

- I. Monthly for 3 months post active study completion – phone follow up with participant.
3. Due to COVID-19 and the need to keep patients and researchers safe, we may use Zoom, a HIPAA compliant, university approved video conferencing software, during the visit. This will allow the participant to smoke freely (unmasked) while the researcher can watch and communicate with the participant via video conferencing from outside the clinic room. We will only enter the room when necessary and will ensure the participant is masked when research staff are present.
4. All procedures, tests, and visits are being performed solely for research purposes and are not billable to insurance.

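### A product-related SAE ends study participation, not only product use, so that participant's later Aim 2 outcomes go uncollected for a reason tied to product harm

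*Protocol*

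**What the plan says.** Section II.L, item 3, gives two rules in consecutive sentences. After an adverse event, participants are reminded that the study is voluntary and will "be allowed to discontinue participation without negative consequences". The next sentence makes leaving compulsory for one class of event: "In the case of SAEs related to use of study products, participation will be discontinued".

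The withdrawal rule in II.D, item 3, concerns failed nicotine abstinence at the first visit. It too takes the person out of the study altogether: "they will be withdrawn from the study (i.e., participants will be rescheduled one time".

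Aim 2 (section I.A) needs outcomes up to Week 12: switch pattern, cardiovascular health, functional activity, lung function and puff pattern. Section V.A analyses continuous outcomes as change from Week 0 to Week 12. On the COPD Assessment Test, II.E says: "Participants will complete the CAT at baseline and Wks 4, 8, and 12 to assess changes in self-reported respiratory health". The 7-day Timeline Followback (TLFB) is taken at Weeks 0, 4, 8 and 12. On exhaled CO, a reading below 6 "ppm will indicate a complete switch".

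Two passages provide contact after treatment. II.L, item 4, promises follow-up for three months post treatment, and II.E.2.l describes monthly phone calls over three months. Neither names an outcome measure.

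**The concern.** Stopping the e-cigarette after it has caused a serious event is plainly right. Stopping observation is a separate decision, and the protocol merges the two. Someone removed after Visit 2 and before Week 12 contributes no later TLFB, eCO, CAT, spirometry, 6-minute walk (6MWD), pulse wave velocity or beat-to-beat blood pressure.

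The loss is tied to harm from the product, and several Aim 2 outcomes are health outcomes, so the people removed may be those whose health worsened. II.C, item 3, continues recruitment until each group has 15 complete cases, with up to 22 recruited. That restores the count but not the information lost. The pilot's stated purpose (V.A) is to supply effect sizes for a larger trial.

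**Working it through.** **Reading the rule.**

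1. Noun: in II.L, item 3, participation in the first sentence means being in the study, since the voluntary nature of the study is the subject. The second sentence repeats the noun with no narrowing to product use.
2. Exceptions: neither the visit descriptions in II.E.2 nor II.L describes a participant who is off product by rule but still assessed.
3. Later contact: phone calls cannot supply eCO, spirometry, 6MWD, pulse wave velocity or blood pressure.
4. Knock-on point: II.E.2.k makes Human Lab Visit 3 a repeat of Visit 1 without training, and Visit 1 (II.E.2.c) includes re-screening against the eligibility criteria. One exclusion is "recent history of cardiovascular or pulmonary events in the past 3 months". The switch period is 12 weeks (12 × 7 = 84 days). A cardiovascular or pulmonary SAE within it therefore falls inside roughly three months of Week 12, and read literally the participant would fail re-screening even if II.L were changed.

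**The plan's own precision.** From II.C, item 3, SD of change = 1.5 seconds and n = 15:

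- 1.96 × 1.5/√15 = 0.759, matching the stated 0.76.
- In SD units: 0.76/1.5 = 0.507, which agrees with 1.96/√15 = 0.506.

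The plan states this margin for puff duration. By the same formula, about 0.51 SD applies to any mean change at n = 15.

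**Illustrative size.** The protocol gives no SAE rate. I assume a product-related SAE risk p of 0.5–2% per participant, and a removed participant whose change differs from the others' mean by d = 1–2 SD.

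| Quantity | Formula | Low | High |
|---|---|---|---|
| Expected events, n = 15 | 15p | 0.075 | 0.30 |
| Chance of at least one, n = 15 | 1 − (1 − p)^15 | 7% | 26% |
| Expected events, n = 22 | 22p | 0.11 | 0.44 |
| Chance of at least one, n = 22 | 1 − (1 − p)^22 | 10% | 36% |
| Shift in mean change, one exit beside 15 completers | d/16 | 0.0625 SD | 0.125 SD |
| Shift as share of half-width | (d/16)/0.507 | 12% | 25% |
| Shift weighted by expected events, n = 15 | 15p × d/16 | 0.005 SD | 0.0375 SD |

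One exit beside 15 completers leaves 1/16 = 6.3% of those participants without Week 12 health outcomes; two leave 2/17 = 11.8%. The 12–25% row applies only if an event has occurred. The weighted shift is about 1–7% of the half-width (0.005/0.507 and 0.0375/0.507).

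**The case against.** The strongest objection is that this does not matter here. The trial is an open-label pilot of 45, described as no more than minimal risk. Both inputs to the size calculation are assumed, and the weighted result is a few hundredths of an SD at most. That stands, and it caps the importance of the point.

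A second objection is that the remedy recovers little. SAEs in II.L include fatal, life-threatening and disabling events and hospitalisations. Many such people could not do a walk test or attend the cardiovascular laboratory, and the three-month event exclusion points the same way. This also largely stands. The realistic gain is TLFB, CAT and eCO, with the other measures only for those cleared and able.

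A third is that ending participation is a conservative safety choice. Stopping exposure is; ending observation adds no protection, provided continued assessment is consented and medically safe.

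A reader might also infer more than the protocol supports:

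- **That anyone who stops vaping is removed.** Not so. II.E.2.c lets participants use the device as much or as little as they like before Visit 2, and switching is itself an outcome. The gap is limited to product-related SAEs. Nor are these the only compulsory exits: the pregnancy exclusion is confirmed at each visit, which implies another.
- **That the switching proportion is biased by a known amount.** That depends on who is in the denominator, which may be settled in an analysis plan not at hand.
- **That the comparison of arms is biased in a known direction.** All arms receive the product, so the direction is unknown.
- **That the primary endpoint is undermined.** It uses Visits 1 and 2, which are 1–5 days apart, so only an SAE before Visit 2 affects it. The fix would not restore that value, because the vaping session rightly stops.
- **That safety contact ceases.** II.L, item 4, most naturally includes people who stopped early, so II.E.2.l needs no rewording on this account.

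**Conclusion.** The point holds as a defect in a stated rule. As written, II.L, item 3, ends study participation after a product-related SAE, and any such event before Week 12 leaves Aim 2 switching and health outcomes uncollected for a reason tied to product harm. Counting rules in an analysis plan could classify the participant for switching but could not supply the unmeasured health values.

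The expected effect is small and cannot be quantified from the protocol. The figure of about 0.005–0.04 SD rests wholly on the assumed SAE risk and the assumed 1–2 SD difference; for a given difference, it scales in proportion to the risk. The change is worth making because it is cheap, not because the pilot's estimates are shown to be at risk.

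**What to change.** In II.L, item 3, replace the instruction to end participation with wording to this effect: *study product will be discontinued; with the participant's consent, scheduled assessments that do not require vaping (at least TLFB, CAT and eCO) will continue; spirometry, 6MWD and the cardiovascular measures will be done only if cleared by the clinician providing medical oversight; and the SAE will be followed until it resolves or stabilises.*

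Add one sentence stating that the Visit 1 re-screening carried into Human Lab Visit 3 does not exclude these participants from the non-vaping assessments.

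The cost is two or three sentences of text, a medical clearance step, and a few contacts on the existing schedule. The Week 12 eCO visit can already be held off site: "Because the eCO is the only measure needed for this visit, visit location will be flexible". II.G says otherwise in general terms ("All study visits will be completed at the Clinical Research Unit"), so the amendment should make clear that the flexible location applies here.

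The downside is that some Week 12 data will be off-product, and should be flagged as such. The eCO threshold confirms only a complete switch, so predominant use would rest on self-report. Puff and nicotine-boost outcomes will stay missing, and the exertional and cardiovascular outcomes often will too.
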